7.4 RECORDING ADVERSE EVENTS

Adverse event assessment and reporting will extend from signing of ICF until completion of the final visit (End of the Posttreatment Period). Adverse events occurring from the time of ICF signing up to the intake of the first dose of study medication will be classified as pre-existing conditions for this study and therefore will be recorded in the Medical History page of the eCRF. If, however, an event is considered a Serious Adverse Event (as defined below), and occurs after the signing of informed consent but before randomization (i.e., during screening), this will be collected and reported as non-treatment-emergent Serious Adverse Events, and will be recorded in the Adverse Event page of the eCRF. Events that occur from time of first dose of study drug until completion of the final study visit will be considered Treatment-Emergent Adverse Events, and recorded on the AE page of the eCRF. Adverse events occurring after the end of the study should be reported to the Sponsor by the Investigator only if the event meets at least one seriousness criterion and the Investigator considers the causal relationship to the study drug as 'reasonably possible'.

All AE reports should contain a brief description of the event, date of onset, date of resolution, intensity, treatment required, relationship to study drug, action taken with the study drug, outcome, and whether the event is classified as serious.

All AEs experienced by patients who are randomized to treatment, regardless of the relationship to study drug, will be recorded in the eCRF. For patients who are screen failures, only SAEs (if any) will be reported on the AE page of the eCRF.

7.5 REPORTING SERIOUS ADVERSE EVENTS

All SAEs that occur during the study, as defined by the protocol, must be reported by the Investigator to the designated SAE Safety Contact by submitting (faxing or emailing) the SAE Form **within 24 hours** from the point in time when the Investigator becomes aware of the SAE. In addition, all SAEs including any deaths, which occur up to and including 30 days after the administration of the last dose of the study medication, must be reported to the designated Safety Contact **within 24 hours**.

All SAEs will be collected and reported from signing of informed consent/assent until the end of the study. All SAEs that occur from signing of the ICF/assent to 30 days after the last dose of study medication must be reported *whether or not considered causally related* to the study medication. Any SAE that occurs beyond 30 days after last dose of study medication must be reported to the designated safety contact only if the event is considered (in the opinion of the Investigator) causally related to the study drug.

SAE forms will be provided to each clinical site. The information collected will include a minimum of the following: protocol number, Investigator information, patient number, event term, a narrative description of the event including its start date, and an assessment by the Investigator as to the intensity and possible relatedness to study medication. A sample of the SAE form can be found in the study manual. The Medical Monitor or Synergy may request follow up information regarding the SAE.

The Investigator will prepare or directly oversee preparation of each SAE report and the Medical Monitor will evaluate and confirm the seriousness and the causal relationship of the event to study treatment. In addition, the Investigator and Medical Monitor will evaluate the expectedness according to the reference document (Investigator Brochure). Based on the Medical Monitor's and Sponsor's assessment of the event, a decision will be made concerning the need for further action.

The initial SAE Report Form must be faxed or emailed by the Investigator to the designated Safety Contact (below) within 24 hours of becoming aware of the event:

SAE REPORTING SAFETY CONTACT INFORMATION
Chiltern Safety and Pharmacovigilance

[REDACTED]

[REDACTED]

[REDACTED]

For any questions related to the reporting of an SAE, sites should call the PV Hotline and include the following information: Sponsor (Synergy Pharmaceuticals), protocol number (SP304202-13), and contact information.

The minimum information required for an initial report is:

- Name of person sending the report (i.e., name and address of Investigator)
- Patient identification (site number, patient number, initials, NOT patient name)
- Protocol number
- Description of SAE
- Causality assessment, if possible

However, as far as possible all points on the SAE form should be covered in the initial report, or the completed SAE form itself must be faxed to the designated Safety Contact. In addition, the event must be documented in the eCRF.

After receipt of the initial report, the Safety Contact and safety center will review the information and, if necessary, contact the Investigator, to obtain further information for assessment of the event. Acknowledgement of receipt of the SAE report will be sent to the site within 24 hrs. In the event acknowledgement is not received, the site should contact Chiltern Safety.

All SAEs must be reported by the Investigator to their IRB/IEC in writing, as well as appropriate regulatory authorities, as required by law. The designated Chiltern Safety Contact will be responsible for all information processing and reporting according to local legal requirements.

7.6 FOLLOW-UP OF ADVERSE EVENTS

All AEs experienced by a patient, irrespective of the suspected causality, will be monitored until the AE (including abnormal laboratory values) has resolved or has returned to baseline or stabilized at a level acceptable to the investigator and medical monitor; until there is a satisfactory explanation for the changes observed; until the patient is lost to follow-up; or until the patient has died. The recording of a stop date is required for all reported adverse events. The handling of a missing AE stop date when a patient is lost to follow-up or when an adverse event is considered stable but ongoing at the end of study visit will be outlined prior to database lock.

7.7 PREGNANCY

Female patients enrolled in the study should make every effort to avoid becoming pregnant during their participation in the study. Female patients should be reminded at every visit to use appropriate birth control methods. However, if a female patient should become pregnant during the study (i.e., from the date the ICF was signed until the patient's last visit), the investigator (or authorized delegate) should notify the designated safety contact and Synergy Pharmaceuticals, Inc., on the initial Pregnancy Report form within 24 hours of the investigator (or authorized delegate) first becoming aware of the pregnancy. Pregnancy itself is not an AE, unless there is suspicion that the investigational product may have interfered with the effectiveness of a contraceptive medication. Pregnancy reports, however, are tracked and reported in the safety (SAE) database but will be reported separately from SAEs. Pregnancy occurring in the patient between the date of the ICF was signed until 30 days after the last dose of study medication will fall under the expedited reporting procedure for serious adverse events. The pregnant patient will be immediately discontinued from the study, but will be followed for the duration of the pregnancy. Details of the outcome of the pregnancy (e.g., full term normal delivery, stillbirth, congenital anomalies, or miscarriage) will be collected and reported by the site.

All reports of congenital abnormalities/birth defects are SAEs. Spontaneous miscarriages should also be reported and handled as SAEs. However, elective abortion without complications should not be handled as SAEs.

All outcomes of pregnancy, if known, must be reported by the Investigator to the Medical Monitor or designated safety contact on the pregnancy outcome report form within 30 days after he/she has gained knowledge of the facts. See **Section 11, Appendix B** for additional details on pregnancy reporting requirements.

8 STATISTICAL METHODS

The objectives of the study are to assess the safety and efficacy of plecanatide 0.5, 1.0, and 1.5 mg dosed daily, compared with placebo.

Before database lock and un-blinding, a formal statistical analysis plan (SAP) will be written and will include details of all statistical methods to be used to analyze the efficacy and safety data. The SAP will supersede the protocol with respect to the analyses specified, although the primary analysis described in this section will remain unchanged.

8.1 RANDOMIZATION AND TREATMENT ASSIGNMENT

This is a double-blind, placebo-controlled study with four treatment arms that will be conducted at approximately 40 clinical sites. Approximately 120 patients will be randomized to receive plecanatide 0.5, 1.0, and 1.5 mg, or the placebo equivalent, in a 1:1:1:1 ratio using an Interactive Web-based Response System (IWRS).

Central, block randomization will be performed with stratification by gender.

8.2 SAMPLE SIZE AND POWER CONSIDERATIONS

Based on data from two phase 3 trials conducted by the sponsor in adults with CIC, assume a mean change from baseline in weekly SBM rate for placebo-treated subjects of 1.2 with a standard deviation of 2.6; similarly, for plecanatide-treated subjects, assume a mean change from baseline of 3.1 with a standard deviation of 4.0. Then, a *t*-test for the difference in means of two independent samples with unequal variances, at a two-sided level of significance of 0.05 and 80% power to detect the assumed difference in means, would require 51 subjects per treatment group. Since study SP304202-13 is being conducted in adolescents with CIC, and the primary analysis of the primary endpoint will be an ANCOVA using a linear mixed-effects model, the sponsor believes that 30 subjects per treatment group (placebo and 3 dose levels of plecanatide), yielding a planned target enrollment of a total of 120 subjects, will prove sufficient for achieving the primary objective of this phase 2 study.

8.3 ANALYSIS POPULATIONS

The following populations will be assessed:

Safety Population: All randomized patients who receive at least one dose of the study drug. Patients will be analyzed according to the treatment received. All safety analyses will be based on the Safety Population.

Intent-to-Treat (ITT) Population : All patients randomized to study treatment. Patients will be analyzed according to the treatment to which they are randomized. The ITT Population is the main population for assessments of efficacy.

Per Protocol (PP) Population: All patients in the ITT population who complete the 8-week Treatment Period or discontinue from study treatment due to adverse event(s) or lack of efficacy, with the exception of major protocol violators. Criteria to identify the PP population will be detailed in the SAP. Decisions regarding exclusion from the PP Population will be made prior to unblinding the database.

Efficacy analyses will be based on the ITT Population. Efficacy analyses will be repeated for the PP Population to assess the sensitivity of the analyses to the choice of analysis set.

Deviations from the study protocol, including violations of inclusion/exclusion criteria, will be assessed as “minor” or “major” in cooperation with the Sponsor. Major deviations from the protocol will lead to the exclusion of a patient from the PP Population and will be determined prior to unblinding the study database.

8.4 GENERAL CONSIDERATIONS

Categorical variables will be summarized by the number and percentage of patients in each category level. Continuous variables will be summarized by number of observations, mean, standard deviation (SD), median, minimum, and maximum values. Where data are collected over time, both the observed data and change from Baseline will be summarized at each time point.

Summaries will be presented by treatment group (placebo, and plecanatide 0.5 mg, 1.0 mg, and 1.5 mg), and combined active doses. All data collected in the eCRF will be presented in listings.

All statistical tests will be two-sided at the 5% level of significance, unless stated otherwise.

No interim analyses are planned.

8.4.1 Missing Data Conventions

In general, data will not be imputed for safety analyses.

The weekly SBM (CSBM) rate is the sum of the SBMs (CSBMs) recorded for the days in the week for which a BM response is recorded in the daily diary. Note that this is equivalent to a “worst case” analysis in that the SBM (CSBM) rate for the week is the sum of the SBMs (CSBMs) recorded for the days in the week for which BMs were reported, plus 0 SBMs (0 CSBMs) for each day in the week for which the BM response is missing. In any week in which no BM response is recorded, the weekly SBM (CSBM) rate will be set to 0 in any summary or linear mixed-effects model analysis involving the weekly SBM (CSBM) rate. In particular, for a randomized patient who withdraws from study participation prior to the end of the study, the patient is considered to have a weekly SBM (CSBM) rate equal to 0 for any weeks remaining in the planned duration of the study for which the patient has no BM responses recorded.

The weekly average CIC-related abdominal pain score is the average of the non-missing, abdominal pain scores recorded in that week, i.e., the weekly average is the sum of the abdominal pain scores recorded in the diary in the given week, divided by the number of pain scores recorded in the week. In any week in which a patient has no diary days for which an abdominal pain score is recorded, the weekly average abdominal pain score will be set to missing. In any linear mixed-effects model analysis involving the weekly average abdominal pain score, if the average score is set to missing in a given week, it will be left as missing in the linear model. In particular, for a randomized patient who withdraws from study participation prior to the end of the study, the weekly average abdominal pain score will be set to missing for any weeks remaining in the planned duration of the study for which the patient has no abdominal pain data.

In any analysis involving abdominal bloating, abdominal discomfort, straining during a bowel movement or pain with defecation, the determination of weekly averages will follow the same methodology as described above for the abdominal pain score. That is, the weekly average item score is the sum of the non-missing scores recorded during the week, divided by the total number of non-missing scores recorded. In any week in which a patient has no non-missing item score recorded, the weekly average score will be set to missing in any summary or linear mixed-effects model analysis involving the weekly average item score.

In any analysis involving stool consistency (BSFS scores), the determination of weekly averages will follow the same methodology as presented above for abdominal pain. However, since stool consistency cannot be assessed if the patient does not have at least one SBM during the week in question (i.e., stool consistency is based on SBMs only), the weekly average will also be set to missing if no SBMs are recorded for any days in the week. Also, it is possible that a patient has no baseline weekly average stool consistency score because of the SBM criterion; in that case the patient will be excluded from any change from baseline analyses of stool consistency.

For the exploratory Responder analyses, in any given week, a patient must have at least 4 compliant diary days in that week. A compliant diary day means that the patient has responded to the BM and rescue medication use questions in the daily diary for that day. Patients who have fewer than 4 compliant diary days in a given week will be considered “non-responders” for that week. Note that this implies that for any week for which a patient has no BM or rescue medication use data, the patient is considered a non-responder; in particular, for a randomized patient who withdraws from study participation prior to the end of the study, the patient is considered a non-responder for any weeks remaining in the planned duration of the study for which the patient has no BM or rescue medication use data.

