Criteria for Evaluation of Efficacy and Safety	
Efficacy endpoints
 
The primary efficacy endpoint is:
 
Proportion of responders for the last 2 weeks of the Treatment Period (responder = a child who experiences >3 SBMs per week for each of the last two weeks of the treatment period) compared to placebo and across treatment groups.
 
The key secondary efficacy endpoints are:
 
Change from Baseline in stool consistency (as assessed by BSFS)Change from Baseline in frequency of SBMsChange from Baseline in frequency of CSBMs 
Additional efficacy endpoints are:
 
Change from Baseline in CIC-related symptoms (abdominal pain, abdominal bloating, abdominal discomfort, straining with a bowel movement and pain with defecation)Frequency/severity of excessive flatulenceFrequency of fecal incontinencePatient Reported Global Assessments (PGA, PAC-SYM and PAC-QOL) 
Pharmacokinetic endpoints
 
Single dose and steady state of plasma plecanatide (population modeling):

	
• Plasma concentration of plecanatide (Note: measurable plecanatide levels have not been observed in the adult population)• PK parameters, including C_{max}, T_{max}, and C_{min} (only if a sufficient number of plecanatide levels can be measured to allow computation of these parameters) 
Safety endpoints
 
• Frequency of treatment-emergent adverse events (TEAEs)• Significant shifts from Baseline values in laboratory analytes and vital signs

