5.2.2 Visit 2: Randomization / Day 1 of Treatment Period

Study eligibility must be confirmed ***prior to randomization***, including the following:

- Confirm that patient has used only study-supplied rescue medication laxative (Dulcolax[®]) since Visit 1
- Urine drug screen (see **Section 4.3.2** for details)
- Urine pregnancy test, if applicable
- Update medical history and concomitant medications, as necessary

The last 14 days of daily diary entries prior to randomization will be used for determination of baseline data. Only patients who meet the protocol criteria for confirmation of CIC and demonstrate diary and RM compliance are eligible for randomization. This eligibility determination will include:

- A review of the baseline diary entries to ensure patients have completed at least 5 of the 7 days of diary entries in each of the 2 weeks of baseline assessments
- A review of the BM frequency data to ensure < 3 SBMs in each of the 2 weeks of the baseline diary assessment period
- A review of rescue medication use to ensure patients have not used RM for more than 2 days in each baseline week

The eligibility determination based on these criteria will be programmed into the IWRS and the system will report out eligibility (the PI or site staff will not be responsible for evaluating diary data to make the diary-based eligibility determination).

The following procedures will be performed ***only for patients eligible for randomization:***

Procedures ***prior to study drug dosing:***

- Physical examination (including body weight) and vital signs (seated blood pressure, heart rate, respiration, and body temperature)
- 12-lead ECG (semi-recumbent)
- Assess adverse events
- Safety laboratory assessments (hematology, serum chemistry, urinalysis)
- Confirm that patient is on a stable diet and has no significant changes in their consumption of liquids or fiber or their level of activity
- Blood samples for plecanatide/SP-338 concentration and immunogenicity assessments (see **Section 4.3.3** for details)
- Have the patient complete all baseline PRO questionnaires (Per Study Procedure Manual).

The first dose of study drug will be administered at the clinical site under supervision. The time of dosing will be recorded.

The following procedures will be performed ***after study drug dosing:***

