8.4.3 Baseline Definition

For each safety parameter, the most recent valid assessment recorded before randomization will be used as the baseline for all analyses of that safety parameter.

For efficacy parameters, the baseline values will be derived from data collected in the 2-week electronic diary assessment at the end of the Screening Period (baseline). The last 14 days of diary entries prior to Day 1 will be the default standard for derivation of these values.

The baseline SBM (CSBM) weekly rate will be the weekly average number of SBMs (CSBMs) recorded during the 2-week baseline assessment period. Baseline stool consistency, severity of straining during a BM, and abdominal symptoms will be calculated as follows: for each week of the baseline assessment, the weekly average is the sum of the non-missing scores recorded during the week divided by the total number of non-missing scores recorded during that week; the baseline is then equal to one-half of the sum of the two weekly average scores..

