8.8.2 Secondary Efficacy Endpoints

The secondary efficacy endpoints, and methods of analysis for each, are:

8.8.2.1 Change from Baseline in Weekly Average Stool Consistency (BSFS) Score Over the 8-week Treatment Period, and by Study Week

The weekly average stool consistency (BSFS) score for each patient will be computed, as described in **Section 8.4.1**, for each week of the 8-week treatment period. The change from baseline in mean weekly average BSFS score over the 8-week treatment period will be analyzed using a linear mixed-effects model with fixed effects for gender (stratification variable), treatment, week, and the corresponding baseline value; a random intercept for patient will also be specified. The least squares (LS) mean change from baseline will be presented, by treatment group, and the difference in LS means for each plecanatide treatment group compared to placebo will be presented, with 95% confidence intervals and corresponding statistical *p*-values.

As a supplement to the above analysis, the weekly average stool consistency (BSFS) score for each patient will be computed, as described in **Section 8.4.1**, for each week of the 8-week treatment period and for the two weeks of the follow-up period. A summary, by treatment group, of the mean weekly average BSFS score, and change from baseline in mean weekly average BSFS score, for each of the 10 study weeks will be presented. The change from baseline in mean weekly average BSFS scores will be analyzed using a linear mixed-effects model with fixed effects for gender (stratification variable), treatment, week, the interaction of treatment and week, and the corresponding baseline value; a random intercept for patient will also be specified. The least squares (LS) mean change from baseline will be presented, by treatment group, and the difference in LS means for each plecanatide treatment group compared to placebo will be presented, with 95% confidence interval and corresponding statistical *p*-value, for each week of the 8-week treatment period and for the two follow-up weeks.

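### Patients with no baseline stool-consistency score enter no BSFS treatment contrast, an avoidable loss of precision and of ITT coverage

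*Combined protocol and SAP*

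**What the plan says.** - The synopsis puts stool consistency first in its list beginning "The key secondary efficacy endpoints are".
- Section 8.8.2.1: "The change from baseline in mean weekly average BSFS score over the 8-week treatment period will be analyzed using a linear mixed-effects model", adjusted for the baseline score. The supplementary by-week model also has change from baseline as its response. The ANCOVA in the synopsis needs a baseline too.
- Section 8.4.1 bases consistency on SBMs, so "the weekly average will also be set to missing if no SBMs are recorded for any days in the week". It foresees that "it is possible that a patient has no baseline weekly average stool consistency score because of the SBM criterion", and rules that "in that case the patient will be excluded from any change from baseline analyses of stool consistency".
- Section 8.4.3 forms each weekly baseline average, and "the baseline is then equal to one-half of the sum of the two weekly average scores". It does not say what happens when only one of the two weeks has a score.
- Section 8.3 defines the ITT population as "All patients randomized to study treatment" and bases the efficacy analyses on it.
- Section 5.2.2 requires "A review of the BM frequency data to ensure < 3 SBMs in each of the 2 weeks" of the baseline diary, and exclusion criterion 19 in Section 3.2 agrees. This is an upper limit only.
- Sections 8.4 and 8.8.2.1 also call for descriptive summaries of the observed weekly scores by arm. The exclusion does not reach these.

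**The concern.** Taken together, these rules allow a patient with no SBM in either baseline week to be randomized and to belong to the ITT population, yet to contribute nothing to any BSFS treatment contrast. Such patients may be among the more constipated in the trial. If they have SBMs on treatment, they have BSFS scores on treatment, and a comparison of arms on those scores does not need every patient's baseline. It is the choice of change from baseline as the response that makes the baseline indispensable. With about 30 patients per arm, information given up in this way is worth keeping. The resulting estimate also describes only patients with a scorable baseline stool, not everyone randomized.

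**Working it through.** **The plan's own figure.** The only sample-size figure is in Section 8.2: 51 per group for the change in weekly SBM rate (difference 3.1 − 1.2 = 1.9; SDs 2.6 and 4.0; two-sided 0.05; 80% power). A t-test with unequal variances gives 79.5% power at 50 and 80.3% at 51 per group, so the figure reproduces. It does not concern BSFS. The plan gives no BSFS sample size and no expected number without a baseline.

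**Who is excluded.** Let f be the share with no baseline BSFS. The documents do not give it, so I assume Poisson SBM counts with mean m per week, independent between the two weeks, and keep only patients with at most 2 in each week (Sections 3.2 and 5.2.2). Here m is the mean before that truncation.

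- P(0 in one week | eligible): p0 = exp(−m) / P(X ≤ 2) = 1/(1 + m + m²/2)
- No SBM in either week: f = p0²
- At least one week without an SBM: 1 − (1 − p0)²
- Largest SE inflation: 1/√(1 − f) − 1

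| m | p0 | f | Of 120 | SE inflation, at most | At least one week without an SBM |
|---|---|---|---|---|---|
| 1.5 | 1/3.625 = 0.276 | 7.6% | 9 | 4% | 48% |
| 1.0 | 1/2.5 = 0.400 | 16.0% | 19 | 9% | 64% |
| 0.75 | 1/2.031 = 0.492 | 24.2% | 29 | 15% | 74% |
| 0.5 | 1/1.625 = 0.615 | 37.9% | 45 | 27% | 85% |

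The last column is the share without a baseline if Section 8.4.3 is read as requiring a score in both weeks. If rates also vary between patients (gamma-Poisson, shape 1 or 2, mean 0.75 to 1.5), f is 24% to 46%.

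**Effect on power.** Take a BSFS contrast that would have 80% power with 30 per arm, and suppose each arm loses the same share. By the normal approximation, power is Φ(2.80√(1 − f) − 1.96).

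| f | Per arm | Power |
|---|---|---|
| 5% | 28.5 | 78% |
| 10% | 27 | 76% |
| 20% | 24 | 71% |
| 30% | 21 | 65% |
| 40% | 18 | 58% |

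**How much can be recovered.** The SE inflation above is an upper bound for each f, because it supposes that every excluded patient could contribute fully. A simulation of 4 × 30 patients checked this, with one on-treatment score each, baseline/on-treatment correlation 0.3 and effect 0.75 SD. It compared ANCOVA in patients with a baseline against ANCOVA keeping everyone with a missing-baseline indicator.

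| f | SE, baseline required | SE, all kept | SE, if 70% of those without a baseline have a score |
|---|---|---|---|
| 20% | 0.279 | 0.251 | 0.259 |
| 30% | 0.301 | 0.253 | 0.265 |

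With all kept, power rises from 76% to 82% at f = 20% and from 68% to 83% at f = 30%. In a null run at f = 20% (correlation 0.4), type I error was 5.1% with a baseline required and 5.4% with the indicator. The simulation did not let the chance of having an on-treatment score depend on arm.

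**The case against.** Much can be said for the plan. It gives its reason: with no rated stool at baseline, no change from baseline can be formed, and the endpoint is defined as a change. The loss is avoidable, but it is not unexplained.

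A reader might infer that these patients' on-treatment scores are collected and thrown away. The documents do not support that, since the weekly descriptive summaries still include them. Nor can it be assumed that the scores are plentiful. Section 8.4.1 sets a week without an SBM to missing, and patients with none in 14 days may have few afterwards.

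A reader might also infer that the rule removes the most severe patients. That too goes beyond the documents. A zero count can arise because a bowel movement within 24 hours of laxative use is not an SBM (Definition of Terms), with rescue allowed on up to 2 days in each baseline week, or because up to two diary days a week may be missing (Section 3.2).

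The remedy has a limit of its own. On-treatment BSFS exists only after an SBM, which the drug is meant to promote, so whether the added patients have scores may depend on their arm. Finally, this is a secondary endpoint in a trial that calls itself exploratory, and f may be small: at 5% to 10% the SE rises by only 3% to 5%.

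All of this stands and limits the size of the point. It does not change the fact that the planned models leave out randomized patients whose available data a different model could use.

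**Conclusion.** The point holds as one of precision and coverage. ITT patients without a baseline BSFS score enter no BSFS treatment contrast, and the plan offers no analysis that retains them. A reader might go further and infer a biased treatment comparison. The documents do not support that: the exclusion depends only on what happened before randomization, so the comparison among those kept is still a randomized one, as the 5.1% type I error illustrates.

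The size rests on an assumed baseline distribution. With only patients who have no SBM in both weeks excluded, it runs from minor (f about 8%, SE at most +4%) to substantial (f about 38%, SE at most +27%), and is less if some of these patients have no on-treatment SBM. The share could be higher if rates vary between patients or if both baseline weeks must have a score, a case that Section 8.4.3 leaves open. This is an inexpensive improvement worth making, not a flaw that invalidates the endpoint.

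**What to change.** Section 8 announces a formal SAP, before lock and unblinding, that may supersede the protocol on all but the primary analysis. The change can be made there:

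- Replace the exclusion by modelling the weekly on-treatment BSFS score as the response. Either include baseline in the response vector with a mean common to all arms, or use baseline as a covariate, set to its overall mean where missing, plus a missing-baseline indicator. These are alternatives resting on different assumptions; choose one in advance.
- Where only one baseline week has a score, use that week as the baseline.
- Report the number without a baseline BSFS score by arm.
- Keep the planned change-from-baseline analysis as a sensitivity analysis.
- State the limits: BSFS is observed only in weeks with an SBM, which treatment may affect, so neither analysis is a full ITT comparison. The common-mean model also assumes that missing scores are missing at random, although for these patients there was no eligible stool to rate.

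The cost is SAP wording, one revised model statement and one extra table row. No new data are needed.
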